6.2.7 Follow-up of Patients with Overcorrection of Sodium

Once discharged, any patient with overcorrection of sodium will be followed in the study as planned except they will not be treated further with study medication. They will be treated with augmented loop diuretic and other diuretics as appropriate. They will return for study visit 2 (Day 3) where they will have repeat determination of serum electrolytes, including serum sodium, as well as BUN and Creatinine. In the unlikely event that they are found to have serum sodium > 18 mEq/L at this visit, they will be considered for per oral hydration or administration of additional intravenous D5W at the discretion of the clinical investigator. They will be seen at Day 8 for evaluation as planned per protocol including repeat determination of serum sodium. They will also have 30 day follow-up as planned.

6.3 Evaluation During Follow-up

6.3.1 Day 3 at 48 hours post study drug administration

Patients will return on study Day 3 at 48 hours after initial administration of study drug. This follow-up evaluation is expected to occur within \pm 2 hours of initial study drug administration on Day 1.

All patients will undergo the following assessments at this time point:

- Directed history and physical examination, focused on signs and symptoms of congestion
- Assessment of the degree of congestion and dyspnea present

- Vital signs (including blood pressure and body weight)
- A blood sample (20 mL) will be collected for assay of routine clinical labs and copeptin determination
- An optional blood sample (30 mL) will also be collected for potential future biomarker and Omic analysis (including RNA)
- A urine sample (5 mL) will be collected for later measurement of biomarkers, electrolytes and osmolarity and other analytes
- Changes in cardiovascular medications
- Assessment for occurrence of heart failure events
- Assessment for adverse events

6.3.2 Day 8 Follow-up

Patients will return on study Day 8 for their last face-to-face visit in the study. This follow-up evaluation is expected to occur within \pm 2 hours of initial study drug administration on Day 1.

- Directed history and physical examination, focused on signs and symptoms of congestion
- Assessment of the degree of congestion and dyspnea present
- Vital signs (including blood pressure and body weight)
- A blood sample (20 mL) will be collected for assay of routine clinical labs and copeptin determination
- An optional blood sample (30 mL) will also be collected for potential future biomarker and Omic analysis (including RNA)
- A urine sample (5 mL) will be collected for later measurement of biomarkers, electrolytes and osmolarity and other analytes
- Changes in cardiovascular medications
- Assessment for occurrence of heart failure events
- Assessment for adverse events

6.3.3 Telephone contact (Day 30)

All study patients will be contacted by telephone on study day 30 (+/- 2 days).

- Review of heart failure symptoms
- Review of changes in cardiovascular medication
- To determine vital status and occurrence of hospitalizations and ED visits.

Completion of this 30 day telephone follow-up will end the patient's participation in the study.

6.3.4 Core Lab Blood Sample Processing

At each study visit, in addition to sending a blood sample to the local site laboratory, plasma, serum, and whole blood samples and a urine sample will be processed and shipped to the UNITE-HF Biomarker and Genomics Core laboratory at UNC. These samples will undergo additional processing as needed and will be stored long-term according the Manual of Operations that will be developed for the study. Whole blood will be processed at the core lab to isolate DNA and RNA which will be stored appropriately for potential long-term analysis. The blood biomarker copeptin will be measured to assess the association with the therapeutic response to tolvaptan after the completion of study enrollment and patient follow-up. The remainder of the samples will be used by study investigators to evaluate the role of specific biomarkers (plus genetic and Omic markers) in the biology and pathophysiology of heart failure and the response to heart failure medications including tolvaptan.

7. Study Endpoints

7.1 Primary Endpoint

The primary endpoint for the study will be change in body weight between patients randomized to tolvaptan versus placebo from baseline to 48 hours with and without stratification for baseline copeptin level.

7.2 Secondary Endpoints – Congestion Indices and Body Weight.

7.2.1 Change in the patient reported visual analog scale for dyspnea from baseline to 48 hours.

7.2.2 Change in loop diuretic dose (mg furosemide) at 48 hours.

7.2.3 Loop Diuretic Adjustment defined as decrease versus no change or increase in loop diuretic dosing at 48 hours.

7.2.4 Change in Loop Diuretic Score defined based on change in loop diuretic dosing.

7.2.5 Change in body weight from baseline to 8 days.

7.3 Exploratory Endpoints

7.3.1 Association of change in Body Weight with Baseline Copeptin by

Randomized Study Arm. Correlation between copeptin concentration at baseline and the change in body weight from baseline to 48 hours in the study patients stratified by randomization to tolvaptan or placebo.

7.3.2. Other Exploratory Endpoints. Planned exploratory endpoints include longitudinal changes in copeptin, renal function, and serum sodium. In addition, other areas of interest that may warrant future analyses include investigation of interrelationships between clinical characteristics and change in the pattern of worsening heart failure during treatment in the study patients.

8. Statistical Analysis of Study Endpoints

8.1 General Aspects of the Study Analysis

8.1.1 Intention to Treat. The primary analysis will be done on an intention-to-treat basis, with patients analyzed as being in the treatment group to which they were randomized.

8.1.2 Missing Data. No imputation will be made for missing study data points.

8.2 Primary Endpoint.

8.2.1 Priority Analysis of Primary Endpoint

The two components of the Primary Endpoint will be ordered by their importance. The priority analysis of the primary study endpoint will be change in body weight between treatment groups at 48 hours without stratification for baseline copeptin.

8.2.2 Second Analysis of the Primary Endpoint

The second analysis of the primary study endpoint will be change in body weight between treatment groups at 48 hours with stratification for baseline copeptin. This approach will stratify study patients into subgroups based on their baseline copeptin level. Change in body weight will be compared between tolvaptan and placebo stratified according to baseline copeptin levels into low and high groups, in a similar manner to that described above for the primary analysis of the primary endpoint. A single prespecified cut point for baseline copeptin will define low and high copeptin in the randomized subgroups. Originally, this cut point was defined as < 10 pmol/L based on the previous pilot study of the relationship of baseline copeptin to tolvaptan response described in the background section of the protocol. However, recent studies in patients with volume overload, suggest that few patients in the current protocol would have values < 10 pmol/L. Therefore, the prespecified cut point will be determined based on blinded analysis of the baseline copeptin levels in the current study. This cut point will be determined taking into consideration the distribution of copeptin levels present in the study population at baseline. Additional cut points may be proposed based on the unrestricted correlation analysis of the changes in body

weight related to baseline copeptin in the randomized subgroups as described below (8.5.4.1). The copeptin guided hypothesis predicts that patients with elevated baseline copeptin who are treated with tolvaptan will have a significantly greater weight loss than placebo treated patients.

Table 2. Analysis of Treatment Effect by Baseline Copeptin

	Tolvaptan + Augmented current loop	Augmented current loop	Change in Body Weight
Baseline Copeptin Level	Low	Low	Weight change will be similar in 2 treatment groups
	High	High	Weight change will be > in Tolvaptan + Augmented current loop

8.3 Secondary Endpoints: Ordered by Clinical Importance.

8.3.1 VAS Score. The highest priority secondary endpoint will be based on the patient reported VAS dyspnea score with comparison of the change in this scale from Visit 1 to Visit 2 by treatment group. Based on previous experience with this scale, the current study will not have statistical power to determine if there is a difference between the tolvaptan and placebo group in VAS dyspnea results. However, this dyspnea score has been widely used in previous trials of acute heart failure and may provide a signal of potential benefit of tolvaptan.

8.3.2 Change in Loop Diuretic Dose at Visit 2. The next highest priority secondary endpoint will be based on changes in loop diuretic dosing in the study patients at Visit 2. Doses of loop diuretic will be converted as necessary to milligram (mg) equivalents of furosemide dose by the following definitions: 1 mg of bumetanide = 40 mg of furosemide and 1 mg of torsemide = 20 mg of furosemide. The difference of interest will be the dose of loop diuretic at the end of Visit 2 minus the dose at the start of Visit 2 (expressed as mg equivalents of furosemide).

8.3.3 Categorical Assessment of Loop Diuretic Use at Visit 2 – Loop Diuretic Adjustment. Clinical experience strongly suggests that changes in dosing of loop diuretics during the trial would be a strong indicator of changes in congestion status. Specifically, a decision to increase loop diuretic dose during Visit 2 would equate to

worsening congestion while a decision to reduce loop dose during Visit 2 would reflect improvement in volume status and less congestion.

During the development of this aspect of the analysis plan (still in the blinded period of the study), the investigators assumed that the pattern of changes in loop dose use would be similar to that of patients with acute heart failure where increases in doses of loop diuretic are typical. Thus, the initial analysis for loop dose adjustment was based on increases in loop dose at Visit 2 or the addition of metolazone.

However, when blinded aggregate study results were reviewed, the opposite pattern was found. The aggregate blinded data revealed that loop doses on the whole decreased rather than increased at Visit 2 and no additional diuretics were added. These observations led to a final analytical approach, where dichotomous response was characterized as favorable when loop doses were decreased and unfavorable when loop doses stayed the same or were increased.

8.3.4 Change in Loop Diuretic Score at Visit 2. A final response analysis based on changes in diuretic use at Visit 2, change in loop diuretic score, will be developed. This scoring system accounts for increases, decreases, and no change in loop diuretic dose to capture the overall pattern of loop diuretic use at 48 hours. This change in loop diuretic score endpoint will be calculated as follows: patients having an increase in loop diuretic dose at Visit 2 will be given a score of 2, patients with no change a score of 0, and patients with a decrease in loop dose at Visit 2 will be given a score of -1. Increases in loop diuretic dose will be given a higher weighting to account for their reflection of treatment failure. Scores for diuretic change will be compared between the two treatment groups as described below.

8.3.5 Change in Body Weight Visit 1 to Visit 3. This secondary endpoint will be change in body weight change from Visit 1 to Visit 3 by treatment group.

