8.5 Statistical Analysis of Study Results

8.5.1 General Statistics. Descriptive statistics will be generated for a comprehensive set of study variables to determine measures of central tendency and dispersion, as well as to characterize the nature of their distributions and whether outliers existed in the data. Continuous values will be reported as mean \pm standard deviation and categorical values as frequencies and percentages.

8.5.2 Analysis of the Primary Endpoint. The comparison of change in body weight from baseline to 48 hours between the two treatment groups constituted the primary endpoint. Hypothesis testing on this between-group change was performed by

nonparametric methods using the Wilcoxon rank-sum test via SAS PROC NPAR1WAY; a two-sided significance level of .05 was applied. This analysis of change in body weight was compared between all tolvaptan treated patients and all placebo treated patients on an intention-to-treat basis. Within-group changes over time were analyzed via the nonparametric Wilcoxon signed-rank test using SAS PROC UNIVARIATE under a two-sided significance level of .05. The second analysis of the primary study endpoint, comparison of change in body weight between treatment groups at 48 hours **with stratification** for baseline copeptin, will be conducted in the same manner as the priority comparison.

8.5.3 Analysis of Secondary Endpoints.

A two-sided significance level of .05 will also be applied to statistical testing of secondary endpoints with no adjustment for multiple comparisons.

8.5.3.1 Changes in VAS Scale. Changes in the VAS dyspnea scale will be analyzed via point estimates and corresponding standard deviations. Supportive between-treatment group comparisons will be conducted via the Wilcoxon rank-sum test.

8.5.3.2 Change in Loop Dose. For this continuous variable (dose of loop diuretic in furosemide mg equivalents) between-group comparisons will be assessed via t-test.

8.5.3.3 Loop Diuretic Adjustment. The Fisher's exact test will be used to assess between-group comparisons for this dichotomous variable.

8.5.3.4 Change in Loop Diuretic Score. For this ordinal variable between-group comparisons will be assessed via t-test.

8.5.3.5 Change in body weight from Visit 1 to Visit 3. This endpoint will be analyzed in a similar fashion as the change in body weight from Visit 1 to Visit 2.

8.5.4 Analysis of Exploratory Endpoints.

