8.5.4.1 Change in Body Weight with Baseline Copeptin by Randomized Study Arm. This endpoint will be evaluated using Spearman Correlation analysis. The correlation coefficient between copeptin concentration at baseline and the change in body weight from baseline to 48 hours in the study patients within each of the two randomized arms (tolvaptan or placebo) will be determined. The two-sided 95% confidence interval will also be constructed. The Spearman correlation approach will be used as it is rank-based and does not make distributional assumptions.

8.5.4.2. Other Exploratory Endpoints. Planned between-group comparisons of continuous variables (copeptin, serum creatinine, and serum sodium) will be assessed via the Wilcoxon rank-sum test or t-test as appropriate.

9. Sample Size and Rationale

9.1 Sample Size.

The study will have a sample size of 40 patients, equally allocated to the two study treatment groups.

9.2 Power Calculation. The study power calculation was based on the primary analysis of the primary endpoint: change in body weight from baseline to 48 hours between the randomized study groups. Using experience in the preceding pilot study (8), a sample size of 40 patients will have 79% power to detect a difference of 1 kilogram in change in body weight between the study treatment groups (augmented loop diuretic + tolvaptan versus augmented loop diuretic alone) at the two-sided .05 significance level.

10. Safety and Adverse Events

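### Section 8.2.2 fixes one blinded copeptin cut point for the second primary analysis, then allows further cut points drawn from weight change by arm without labelling comparisons at those cuts exploratory

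*Combined protocol and SAP*

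**What the plan says.** Section 8.2.2 compares 48-hour weight change between arms in low and high copeptin groups. It commits to one threshold: "A single prespecified cut point for baseline copeptin will define low and high copeptin in the randomized subgroups". The pilot threshold of 10 pmol/L is set aside because few patients are now expected to fall below it. In its place, "the prespecified cut point will be determined based on blinded analysis of the baseline copeptin levels in the current study". The value itself is not given. Section 2 explains that copeptin is assayed only after the study is completed.

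The paragraph then continues: "Additional cut points may be proposed based on the unrestricted correlation analysis of the changes in body" weight against baseline copeptin in the two randomized groups, with a pointer to 8.5.4.1. It closes with the prediction, tabulated in Table 2, that tolvaptan outperforms placebo when copeptin is high and that the arms are similar when it is low.

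Section 8.5.4.1 takes the Spearman correlation of baseline copeptin with 48-hour weight change "in the study patients within each of the two randomized arms (tolvaptan or placebo) will be determined". Section 7.3.1 lists the same correlation, "in the study patients stratified by randomization to tolvaptan or placebo", among the exploratory endpoints, and the analysis falls under the heading "8.5.4 Analysis of Exploratory Endpoints".

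On testing, 8.5.2 says that the stratified comparison "for baseline copeptin, will be conducted in the same manner as the priority comparison", meaning a Wilcoxon rank-sum test at two-sided .05. Section 8.2.1 places the unstratified comparison first: "The two components of the Primary Endpoint will be ordered by their importance".

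**The concern.** The two kinds of cut point in 8.2.2 are very different. The first uses only pooled baseline copeptin and cannot be influenced by treatment response, so it is sound. The second uses the primary outcome split by arm, so it can be neither blinded nor prespecified. A treatment comparison at such a cut, on the same 40 patients that suggested it, favours the result that prompted it.

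The exploratory label covers the correlation coefficient and its interval. Sections 7.3.1, 8.2.2, 8.5.2 and 8.5.4.1 do not extend it to between-arm comparisons at cuts derived from that correlation, and none limits how many cuts may be tried. The permission also sits under the primary endpoint, directly before the copeptin prediction. At stake is the second of the two hypotheses in the synopsis, that copeptin predicts the degree of benefit from tolvaptan.

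**Working it through.** **Inputs.** 40 patients, 20 per arm (9.1); two-sided .05 and Wilcoxon rank-sum (8.5.2); difference of 1 kg (9.2). Section 9.2 states no SD. I assume 1.1 kg, the all-patient pilot value in Table 1. Also assumed: normal data, no missing values, copeptin unrelated to weight change, and a median cut on pooled copeptin, which gives 40 × 0.5 = 20 patients per stratum, about 10 per arm.

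**The plan's own figure.** The noncentrality is 1 / (1.1 × √(2/20)) = 2.875. With 38 degrees of freedom, t-test power is 80.0%. Scaling n by the Wilcoxon efficiency 3/π gives 78.1%, and simulation gives 77.8%. The stated 79% is reproduced to within about a point. With SD 1.0 or 1.2 kg, t-test power would be 86.9% or 72.9%. Nothing in this point disputes the 79%.

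**Size at one locked cut.** The exact Wilcoxon size at 20 v 20 is 4.91%. For the high stratum, average the exact size over the possible arm splits: Σ P(k) × size(k, 20−k), with k hypergeometric (20 drawn from 40, of whom 20 are on tolvaptan). The result is 4.56%.

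**No drug effect, more cuts.** Count a trial if any examined cut gives p<.05 in the high stratum. Cuts are evenly spaced between the percentiles shown.

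| Cuts examined | 200,000 trials | 4,000 trials |
|---|---|---|
| 1 (median) | 4.6% | 4.6% |
| 3 (40th to 60th) | 8.2% | 8.0% |
| 5 (30th to 70th) | 11.5% | 11.3% |
| 11 (25th to 75th) | 14.7% | 14.2% |

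A separate 4,000-trial run with different placements gave 4.4% at the median alone, 6.7% with one further cut, 8.8% with two, and 13.8% for the best of nine between the 30th and 70th percentiles. Even one extra cut is visible.

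**Uniform 1 kg effect.** This scenario bears more directly on the copeptin claim: tolvaptan works equally in everyone, so copeptin predicts nothing. At a median cut each stratum has 43.8% power. If the strata are treated as independent, the high stratum is significant and the low is not with probability 0.438 × (1 − 0.438) = 0.246; simulation gives about 24%. The chance of seeing that pattern at one or more of the examined cuts (4,000 trials per setting) is:

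| Cuts examined | False pattern |
|---|---|
| 1 | 24% |
| 3 | 41% |
| 5 | 55% |
| 11 | 65% |

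The simulation standard error at 41% is √(0.41 × 0.59 / 4000) = 0.8 points, so the increase is not simulation noise.

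**The case against.** The best defence is textual. The single blinded cut is what defines the analysis. The disputed sentence says only that others may be proposed, not that they will be tested, will replace the blinded cut or will support a primary claim. It also points to a section headed exploratory. This stands in part: a hypothesis-generating reading is natural, and a reader who inferred that the plan declares confirmatory tests at outcome-derived cuts would go beyond the text. What remains is a permission placed inside the primary endpoint with the status of its results left open.

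A second objection is that the simulations assume what the documents do not give. That also stands. No rule turns a Spearman coefficient into a cut point, and fixed percentile grids only stand in for one. The figures show direction and plausible scale, not the trial's error rate. Nor does locking the cut cure everything: the false pattern already occurs in about 24% of trials at one cut, because significance in one stratum and not the other is weak evidence of effect modification.

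Two further inferences are tempting and unsupported. One is that 8.2.2 contradicts the statement in section 2 that plan changes preceded unblinding. That statement concerns changes already made to the plan; proposing a cut later under an existing sentence is not such a change. The other is that the main result is compromised because 8.2.1 ranks the two analyses without an alpha rule. The priority test keeps its own size of about 4.9%. Whether to add a rule is a trade-off between the two analyses for the sponsor to weigh, and it is no part of this point.

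**Conclusion.** The point holds as a gap in status that should be fixed. Section 8.2.2 opens an explicit route from weight change by arm to new copeptin cuts, without a limit on number and without saying that comparisons at those cuts are exploratory. Under the stated assumptions, using that route would roughly double to triple the high-stratum false-positive rate (about 4.6% to about 8% with 3 cuts and 14% with 11). Under a uniform effect it would raise the false copeptin pattern from about 24% to between 41% and 65%. These sizes depend on the assumed SD of 1.1 kg and on the assumed number and placement of cuts. The wording gap does not. The blinded cut is acceptable as planned, and the unstratified priority test, the sample size and the stated power are untouched.

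**What to change.** 1. Move the sentence on additional cut points out of 8.2.2 and into 7.3.1/8.5.4.1.
2. State in 8.2.2 that the second primary analysis uses only the single cut point set from blinded baseline copeptin, with its value recorded and dated before treatment codes are released. The date matters because the pilot value has been dropped and the assays come only after study completion.
3. State that any comparison at a cut derived from weight-change data is exploratory, is reported with estimates, 95% intervals and the number of cuts examined, and supports no primary-endpoint claim.

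The cost is that results at alternative cuts lose any confirmatory standing. Exploration stays open, and no patient, test or power figure changes.

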5.4 Treatment Arms

Patients will be randomized in a 1:1 fashion to one of two types of treatment:

- Augmentation of current dose of loop diuretic + 30 mg of oral tolvaptan daily
 - Or
 - Augmentation of current dose of loop diuretic + placebo for tolvaptan

Doses of loop diuretics will be standardized to mg equivalents of furosemide based on 40 mg of furosemide for each 1 mg of bumex and 2 mg of furosemide for each 1 mg of torsemide. Augmentation of current dose of loop diuretic will be defined as doubling the current dose of oral loop diuretic if the total daily dose of loop diuretic is \leq 120 mg furosemide equivalents. If the total current oral dose of loop diuretic is $>$ 120 mg then the augmented dose of will be 50% of the current oral dose of loop diuretic + the current oral dose of loop diuretic in furosemide mg equivalents.

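### Torsemide is converted to furosemide at 20:1 in section 8.3.2 but at 2:1 in section 5.4; the likely error is in 8.3.2, which sets the scale of secondary endpoint 7.2.2

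*Combined protocol and SAP*

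**What the plan says.** Two sections put loop diuretic doses on a common furosemide scale.

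- Section 5.4 (Treatment Arms) uses "2 mg of furosemide for each 1 mg of torsemide". The augmentation rule depends on that scale. Augmentation is "defined as doubling the current dose of oral loop diuretic if the total daily dose of loop diuretic is" at or below 120 mg furosemide equivalents; above 120 mg the dose rises by 50%.
- Section 8.3.2 (Change in Loop Diuretic Dose at Visit 2) uses "1 mg of torsemide = 20 mg of furosemide". The quantity analysed is the "dose of loop diuretic at the end of Visit 2 minus the dose at the start of Visit 2", in furosemide equivalents.

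Both sections equate 1 mg of bumetanide with 40 mg of furosemide. The 8.3.2 quantity is secondary endpoint 7.2.2, "Change in loop diuretic dose (mg furosemide) at 48 hours", ranked second after VAS dyspnea. Section 8.5.3.2 gives the test: "For this continuous variable (dose of loop diuretic in furosemide mg equivalents) between-group comparisons will be assessed via t-test". Under 8.5.3, two-sided 0.05 is "applied to statistical testing of secondary endpoints with no adjustment for multiple comparisons". Section 9.2 covers weight only: "The study power calculation was based on the primary analysis of the primary endpoint".

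**The concern.** The two torsemide factors differ tenfold and cannot both be right. The account in section 2 of changes to the analysis plan does not mention a revised conversion.

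The factor matters because 7.2.2 is analysed as a mean in mg equivalents. Means, standard deviations and t-tests depend on scale, so a factor ten times too large lets one or two torsemide patients dominate the comparison. If 20 were the correct figure, the fault would lie in the dosing rule of 5.4 instead, and torsemide patients would have been augmented on the wrong side of the 120 mg threshold.

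**Working it through.** **Inputs from the documents.** Torsemide factor 2 (5.4) and 20 (8.3.2); bumetanide factor 40 (both); threshold 120 mg equivalents (5.4); 40 patients, equal allocation, so 20 per arm (9.1); t-test (8.5.3.2) at two-sided 0.05 (8.5.3).

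**Which factor fits the rest of the protocol?**

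| Quantity | Factor 2 | Factor 20 |
|---|---|---|
| Torsemide dose at the 120 mg threshold | 120/2 = 60 mg/day | 120/20 = 6 mg/day |
| Torsemide equal to 1 mg bumetanide | 40/2 = 20 mg | 40/20 = 2 mg |

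At factor 20 the doubling rule would apply only to torsemide doses of 6 mg/day or less. A stray zero in 8.3.2 is the simpler explanation, but this is an inference.

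**Effect of one patient, from the text alone.** A 20 mg torsemide cut scores 20 × 2 = 40 mg or 20 × 20 = 400 mg. Divided by 20 patients, it moves the arm mean by 2 mg or 20 mg.

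**Illustration of the t-test (assumed pattern).** Let 12 of 20 tolvaptan patients and 5 of 20 placebo patients cut 40 mg equivalents, with no change in the others. One of the cutters takes torsemide and cuts 20 mg, which is 40 mg equivalents at factor 2.

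| Case | Tolvaptan mean | Placebo mean | Difference | p |
|---|---|---|---|---|
| Factor 2 | -(12 × 40)/20 = -24 | -(5 × 40)/20 = -10 | -14 mg | 0.025 |
| Factor 20, torsemide patient on placebo | -24 | -(4 × 40 + 400)/20 = -28 | +4 mg | 0.85 |
| Factor 20, torsemide patient on tolvaptan | -(11 × 40 + 400)/20 = -42 | -10 | -32 mg | 0.11 |

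The loss of significance comes from the SD. In an arm of 20 where 10 cut 40 mg equivalents, the SD is 20.5 mg; with one of those ten on torsemide at factor 20, it is 87.5 mg. The larger difference in the last row therefore still has a larger p-value than the factor 2 case.

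**Simulation (all inputs assumed).** 20,000 replicates, 20 per arm. Home dose is drawn evenly from 20, 40, 80, 120 and 160 mg equivalents and augmented by the 5.4 rule; a cut returns the patient to the home dose; the t-test is pooled. Power uses cuts in 60% versus 25% of patients; type I error uses cuts in 40% of both arms.

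| Torsemide share | Power, factor 2 | Power, factor 20 | Type I, factor 2 | Type I, factor 20 |
|---|---|---|---|---|
| 2% | .481 | .385 | .047 | .040 |
| 5% | .485 | .288 | .051 | .028 |
| 15% | .475 | .193 | .051 | .019 |
| 30% | .473 | .212 | .052 | .032 |
| 50% | .474 | .271 | .052 | .046 |
| 75% | .478 | .369 | .049 | .047 |

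At a share of 0% or 100% the factors do not differ beyond simulation noise. A separate simulation assumed normally distributed changes (means -40 and 0 mg, SD 40 mg, torsemide shares 10-50%). Power was about 87% at factor 2 and 41-61% at factor 20. The levels differ with the assumptions; the direction does not.

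**Direction-based endpoints.** 7.2.3 and 7.2.4 use only whether the dose rose, fell or stayed the same, so a common factor cancels unless the patient changes agent. A switch from 80 mg furosemide to 20 mg torsemide is 20 × 2 - 80 = -40 mg (score -1) or 20 × 20 - 80 = +320 mg (score 2).

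**If 20 were right.** A patient on 40 mg/day torsemide counts as 80 mg under 5.4 and is doubled to 80 mg/day. At factor 20 the same dose counts as 800 mg and should rise by 50% to 60 mg/day.

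**The case against.** The contradiction itself is not in dispute. The case for giving it little weight has five parts.

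- **Attribution.** No passage gives a usual torsemide dose, so calling a 6 mg/day threshold implausible draws on clinical knowledge outside the documents. This stands: the text proves only the disagreement, and the clinical team must confirm the factor.
- **Actual effect.** The number of torsemide users is not given and could be zero. At a 2% share, the chance of none among 40 patients is 0.98^40, about 45%. This also stands. The p-values and power figures are illustrations, not estimates for this trial.
- **Reach.** One secondary endpoint is directly affected, in a small trial that the protocol itself calls a pilot. VAS dyspnea and both weight endpoints never use the conversion. That limits the severity but does not remove the fault.
- **Safeguard.** Section 8.5.1 plans to describe distributions and outliers, so a value of -400 mg might be queried. It might, but a programmer following 8.3.2 would find that it agrees with the stated definition.
- **Timing.** Section 8.5.2 describes the primary test partly in the past tense, so the blinded window may have closed. Section 2 says only that changes to the plan preceded unblinding. The fix should allow for both cases.

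**Conclusion.** The concern holds and should be fixed. The plan gives two torsemide factors that differ tenfold, and at least one is wrong. The likelier error is the 20 in 8.3.2; on that reading dosing under 5.4 is sound and only 7.2.2 is mis-scaled.

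The certain part of the size is that each torsemide change counts ten times as much under 8.3.2 as under 5.4. The likely harm is a distorted estimate and lost power, not false positives. How much power is lost depends on the assumed cut rates, doses and torsemide share. The primary endpoint and its power calculation are unaffected, 7.2.3 and 7.2.4 change only if a patient switched agent, and with no torsemide users the analysis does not change.

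**What to change.** Before unblinding, have the clinical team confirm one torsemide factor and state it identically in 5.4 and 8.3.2, most likely by changing 20 to 2 in 8.3.2. Check that the analysis program uses it. Compute 7.2.2 from the recorded agent and dose, and re-check the direction in 7.2.3 and 7.2.4 for any patient who switched agent.

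If 20 is confirmed instead, correct 5.4 and record that torsemide patients above 6 and up to 60 mg/day were augmented under a protocol error, not a site deviation.

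If the data are already unblinded, disclose which factor was programmed and report 7.2.2 with the confirmed one.

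The cost is one corrected number and a check of torsemide users among 40 patients. Diuretic type and dose are already collected (section 2, on changes in loop diuretic), so no new data are needed.
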